6.9.3.2 Imputation of Previous and Concomitant Medication Dates

For previous and concomitant medications, a missing or incomplete start and stop dates will be imputed according to the following conventions:

Start Date Scenario	Convention
Missing day	first day of the month under consideration
Missing month	January
Missing year	year of the informed consent date
Completely missing	Informed consent date

Stop Date Scenario	Convention
Missing day and not ongoing	last day of the month under consideration
Missing month and not ongoing	December
(Missing year or completely missing) and not ongoing	December 31st, 2099
Ongoing	Remains missing

If the above imputed start date is after the stop date, then the imputed start date will be one day prior to the stop date.

6.9.3.3 Imputation of Study Drug Start Date

For the randomized subjects that received study drug, a missing or partial first dose date of study drug will be imputed as the non-missing dispense date at randomization.

6.9.3.4 Onset Date of CTMP

Onset Date Scenario	Convention
Missing day, but month and year are present	the day will be imputed as the 15th day of the month
Missing day and month, but year is present	the day and month will be imputed as 30 June of the year
Missing year, but day and month are present	No imputations will occur, and the subject will be excluded from all summaries related to CTMP duration
Completely missing	Informed consent date

If the above imputed date falls after the informed consent date, then the onset date will be taken as equal to the informed consent date.

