2 INTRODUCTION

2.1 Background

Target Disease

Chronic Tympanic Membrane Perforation (CTMP) is defined as stable maintenance of tympanic membrane perforation over 3 months, in contrast to acute tympanic membrane perforations, which heal within 7 to 10 days [Seonwoo et al, 2013]. CTMP affects both pediatric and adult patients and can result from disease, trauma, or medical procedures. Due to the continuous opening in the tympanic membrane, chronic perforation is usually attributed to chronic inflammation in the middle ear, resulting in suppurative otitis media [Seonwoo et al, 2013; Aggarwal et al, 2006]. Surgical repairs such as myringoplasty or tympanoplasty are employed and are currently the main treatments for patients with CTMP. Successful tympanic membrane closure rates vary between studies, ranging from 35% to 99% [Aggarwal et al, 2006]. Disadvantages associated with these surgical procedures include anesthesia-associated risks and the inconvenience of surgery. Therefore, a non-invasive treatment is desired in order to address the unmet need.

ASP0598 and Its Pharmacological Concept

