5.1 Inclusion Criteria

A subject is eligible for the study if all the following apply:

1. Institutional Review Board (IRB)/Independent Ethics Committee (IEC) approved written Informed Consent and privacy language as per national regulation (e.g., Health Insurance Portability and Accountability Authorization for US sites) must be obtained from the subject or legally authorized representative prior to any study-related procedures (including withdrawal of prohibited medication, if applicable).
2. Subject must be 18 to 75 years of age at the time of informed consent.
3. Subject has chronic tympanic membrane perforation (CTMP) documented as persisting longer than 3 months.
4. A female subject is eligible to participate if she is not pregnant see Appendix [12.3: Contraception Requirements](#) and at least one of the following conditions applies:
 - a. Not a woman of childbearing potential (WOCBP) as defined in Appendix [12.3: Contraception Requirements](#) OR
 - b. WOCBP who agrees to follow the contraceptive guidance as defined in Appendix [12.3: Contraception Requirements](#) starting at screening and for at least 28 days after investigational product (IP) application.
5. Female subject must agree not to breastfeed starting at drug application on Day 1 and for at least 28 days after IP application.
6. Female subject must not donate ova starting on Day 1 and for at least 28 days after IP application.
7. A male subject with female partner(s) of child-bearing potential must agree to use contraception starting on Day 1 and for at least 28 days after IP application as detailed in Appendix [12.3](#).
8. A male subject must not donate sperm starting on Day 1 and for at least 28 days after IP application.
9. Male subject with a pregnant or breastfeeding partner(s) must agree to remain abstinent or use a condom from Day 1 and for at least 28 days after IP application.
10. Subject must be willing and able to comply with the study requirements including refraining from using prohibited concomitant medications.
11. Subject agrees not to participate in another interventional study during the study period.

12. Subject has the ability to understand and the willingness to sign a written informed consent document.

Waivers to the inclusion criteria will NOT be allowed.

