6.2.3 Demographic and Other Baseline Characteristics

Demographics and baseline characteristics will be summarized using descriptive statistics for all randomized subjects, SAF and FAS by treatment group, ASP0598 total (if applicable) and ‘total’ over all treatment groups.

Demographics variables:

Variable	Variable Type	Categories
Sex	Categorical	
• Male• Female• Unknown
Race	Categorical	
• White• Black or African American• Asian• American Indian or Alaska Native• Native Hawaiian or Other Pacific Islander• Other
Ethnicity	Categorical	
• Not Hispanic or Latino• Hispanic or Latino
Table continued on next page		

Variable	Variable Type	Categories
Age	Continuous	NA
Age Group	Categorical	
 • ≤ 60 years • > 60 years
EudraCT Age Category	Categorical	
 • ≥ 18 to ≤ 64 years • ≥ 65 years to ≤ 84 years
Baseline weight	Continuous	NA
Height	Continuous	NA
Baseline body mass index (BMI)	Continuous	NA
Baseline BMI group	Categorical	
 • $\leq 30 \text{ kg/m}^2$ • $> 30 \text{ kg/m}^2$
Primary Diagnosis:		
Onset of chronic tympanic membrane perforation (CTMP) (years) derived as (Informed consent date - onset date of CTMP)/365.25. Imputed date for onset date of CTMP may be used to calculate the onset of CTMP (Section 6.9.3.4).	Continuous	NA
CTMP duration group	Categorical	
 • ≤ 1 year • > 1 year 
 ○ > 1 to ≤ 10 years ○ > 10 years
TMP present	Categorical	
 • Left ear • Right ear • Both ears
Treated ear	Categorical	
 • Left ear • Right ear
Primary Cause of TMP	Categorical	
 • Infection (CSOM) • Trauma • Placement of tube • Iatrogenic complication • Other
Table continued on next page		

Variable	Variable Type	Categories
Areas of tympanic membrane involved in TMP	Categorical	
 • Anterior superior • Anterior inferior • Posterior superior • Posterior inferior • Anterior Superior/ Anterior Inferior • Anterior Inferior/ Posterior Inferior • Posterior Superior/ Posterior Inferior
Areas of tympanic membrane involved in TMP group	Categorical	
 • 1 • 2 • ≥ 3 
Derived as number of areas of tympanic membrane involved in TMP.

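### A completely missing CTMP onset date is set to the consent date, giving a duration of 0.00 years that the entry criterion rules out

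*SAP*

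**What the plan says.** SAP 6.2.3 lists time since onset of CTMP, in years, as a baseline variable, "derived as (Informed consent date - onset date of CTMP)/365.25". It adds: "Imputed date for onset date of CTMP may be used to calculate the onset of CTMP". The same section groups the result as ≤ 1 year, > 1 to ≤ 10 years and > 10 years. SAP 6.4 uses these groups as one of the subgroups in which complete closure is tabulated in the expansion parts, and Protocol 9.4.2.3 lists the same subgroup.

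SAP 6.9.3.4 gives the date rules:

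- Day missing: the 15th of the month.
- Day and month missing: 30 June of the year.
- Year missing, day and month present: "No imputations will occur, and the subject will be excluded from all summaries related to CTMP duration".
- Nothing known: "Completely missing Informed consent date".
- Any imputed date that falls after consent: "the onset date will be taken as equal to the informed consent date".

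Protocol 5.1, criterion 3, admits a subject only with a perforation "documented as persisting longer than 3 months", and the section allows no waivers. Protocol 2.1 describes the disease in the same terms: "defined as stable maintenance of tympanic membrane perforation over 3 months".

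**The concern.** A rule for missing data should give either a plausible value or none. The row for a completely missing onset gives one specific value that lies outside the range the entry criteria permit. It does so for the subjects about whom the record says least, and it is not neutral between groups: it always selects the shortest-duration category.

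At stake are the mean, minimum and distribution of disease duration at baseline, and the make-up of the ≤ 1 year row of the closure subgroup table. With groups of 13, 6 or 4 subjects, one false zero is visible in both places.

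**Working it through.** **Inputs.** The duration formula and groups are from SAP 6.2.3, the imputation rows from SAP 6.9.3.4, and the minimum duration of more than 3 months from Protocol 5.1. The screening period of up to 28 days and the group sizes (13 per expansion arm, 6 active per MAD cohort, 4 active per SAD cohort) are from Protocol 4.1. The plan states no figure for this variable, so there is none to reproduce.

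**Step 1: the value the rule gives.** Onset = consent, so (consent − consent)/365.25 = 0.00 years, which falls in ≤ 1 year in every case.

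**Step 2: the smallest value an eligible subject can have.** Take 3 months as 91 days.

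- Criterion judged at consent: more than 91/365.25 = 0.249 years.
- Criterion judged only on Day 1, after the longest screening period: more than (91 − 28)/365.25 = 63/365.25 = 0.172 years.

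Zero is excluded on both readings.

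**Step 3: effect on a group mean.** Let T be the true duration of one affected subject in a group of n. The mean is lowered by T/n. T is not in the documents, so the values below are assumptions; the plan's own > 10 years category shows that long durations are expected.

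| T (years) | n = 13 | n = 6 | n = 4 |
|---|---|---|---|
| 0.25 | 0.02 | 0.04 | 0.06 |
| 1 | 0.08 | 0.17 | 0.25 |
| 10 | 0.77 | 1.67 | 2.50 |

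**Step 4: effect on the categories.** If T is at most 1 year, the group is right and only the value is wrong. If T exceeds 1 year, the subject is in the wrong group. One, two or three such subjects are 1/13 = 7.7%, 2/13 = 15.4% or 3/13 = 23.1% of an expansion arm.

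**Step 5: the cap, checked separately.** The cap can also return zero, but only for partial dates.

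- Only the year known, equal to the consent year, with consent before 30 June: the true duration is at most the time from 1 January to 30 June, 181 days in a leap year, or 181/365.25 = 0.496 years. The ≤ 1 year group is correct and the error is under half a year.
- Month and year known: the 15th falls after consent only if the recorded onset month is the consent month or later. Onset within the consent month, before consent and before the 15th, is under 15 days at consent and under 15 + 28 = 43 days on Day 1, so that subject fails criterion 3 anyway.

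The cap therefore moves no eligible subject between groups.

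**Step 6: where duration enters the analysis.** The stratification factor at randomization is TMP size (Protocol 6.3.6). The Mantel–Haenszel test adjusts for baseline perforation size, and the repeated-measures model uses the baseline value of the outcome (SAP 6.4.2). Duration is in none of these.

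**The case against.** The strongest reply is that this hardly matters. Duration is a descriptor; the closure subgroups are counts and percentages without tests; and listings show actual partial dates, not imputed ones (Protocol 9.11), so a missing onset stays visible. The case may also be rare: criterion 3 requires documented persistence, and Protocol 10.2.3 calls for a complete history of the target disease, which will often supply at least a year. All of this stands, and it limits the size of the point. It does not make the value right, and documented persistence beyond 3 months does not require a known onset date.

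One could also read onset of CTMP as the day the perforation became chronic, so that a zero is just possible. Protocol 9.11 describes the quantity as time since onset of the perforation itself, which does not support that reading.

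The contrast with the missing-year row should not be pressed too far. A day and month without a year say almost nothing about a duration in years, so that subject is scarcely better documented. The contrast shows only that the table already accepts exclusion when duration cannot be known.

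A reader might go further and infer that the rule shifts long-standing perforations into the shortest group, on the ground that old perforations are the ones without a recorded onset. That is plausible, but nothing in the protocol or SAP says so; it is an assumption. A reader might also blame the cap sentence for errors of 10 years or more. Step 5 shows that it cannot produce them.

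**Conclusion.** The point holds for one row of the table. A completely missing onset date yields 0.00 years, against a minimum of 0.249 years (0.172 on the most lenient reading) for any eligible subject, and places the subject in the ≤ 1 year group regardless of the truth.

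The consequence is confined to the baseline duration summaries and the descriptive closure subgroup by duration. No hypothesis test, confidence interval for the treatment difference, or sample size is affected. A reader might infer a bias in the efficacy result; the documents do not support that, because duration enters no model or stratum.

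The size depends on two unknowns: how many subjects lack any onset date, and their true durations. With one subject and an assumed true duration of 10 years, the mean of an expansion arm falls by 0.77 years; with 0.25 years it falls by 0.02. This is a minor correction, worth making because the stated rule produces a false value and the repair is almost free.

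**What to change.** In SAP 6.9.3.4, change the row for a completely missing onset date to match the missing-year row: no imputation, and exclusion of the subject from all summaries related to CTMP duration, including the duration subgroup for closure. Report the number of subjects with missing duration, by treatment group, beside those summaries. SAP 6.1 already bases percentages on non-missing data, so no new convention is needed.

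Leave the cap as it is. Moving it to 3 months before consent may look like a natural companion change, but it could override a recorded onset month and so hide a breach of criterion 3, which should appear as an entry-criteria deviation (PD1, SAP 6.2.2).

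The cost is one table row, one line in the derivation program and one count in the output. SAP 1 requires changes to the dose escalation part to be approved before those data are unblinded for the interim analysis. If that time has passed for a part, the change can be documented in the clinical study report.

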6.9.3.5 Discontinuation-Reason based MI

The MMRM analysis that will be used to perform the primary analysis of the secondary endpoints assumes that missingness is at random. That is, the model assumes that the trajectory of TMP size (or ratio of TMP size per total area of tympanic membrane) over time for subjects who withdrew the study is similar to the trajectory for those observed in their own treatment group which is valid so long as that assumption is reasonable.

Discontinuation-reason based MI will be used to examine the sensitivity of the primary analysis results to departures from that underlying assumption and will assess a situation where data for subjects who discontinue early follow a pattern which is missing not at random.

First Markov chain Monte Carlo (MCMC) method will be used to partially impute non-monotone missing data for completed and discontinued subjects from the study investigational period for each treatment group separately. After this is done, MI will be used to impute the monotone missing data for the subjects discontinue the study investigational period as follows:

MI will be used for imputation of any missing data, using “Jump to Reference” algorithm (where placebo is the reference group) [Carpenter et al. 2013] under the assumption of MNAR for subjects who discontinue due to lack of efficacy or AEs and standard regression based MI under the assumption of MAR for subjects with missing data for other reasons. The analysis will be implemented using the general three-step process (imputation phase, analysis phase and pooling phase) described in O’Kelly and Ratitch, 2014.

1. The imputation phase will implement MI via sequential modelling for both the “Jump to Reference” algorithm and standard regression-based MI. In particular, when implementing the “Jump to Reference” algorithm via sequential modelling, only baseline values are used in the imputation of missing values for subjects in the ASP0598 active groups who discontinue study investigational period due to lack of efficacy or AEs (this variation of the “Jump to Reference” algorithm is also referred to as the “Unconditional Reference” approach). The imputation phase will generate M imputed datasets, where M =100.
2. The analysis phase will perform the primary MMRM analysis model of the change from baseline secondary efficacy endpoints as described in Section [6.4.2](#) for each of the M = 100 imputed datasets (which now contain complete data, where missing data have been filled in).
3. Rubin’s rules will be used to generate an overall set of pooled results which combines the analysis results from the M = 100 imputed datasets.

7 REVISION AND RATIONALE

7.1 List of Changes in SAP Version 3.0 from Version 2.0

The changes from the approved SAP from Version 2.0 (Dated 22-Nov-2020) to Version 3.0 (Dated 06-Jul 2022) that impact analyses are listed with the rationale in the table below.

SAP Sections	Description	Rationale
4.1	Changed definition of FAS to match protocol	The protocol changed the definition of the FAS to account for
5.4, Table 1, Table 2, 6.5.2, 6.5.3, 6.5.4, 6.6, Table 4, Table 6	Changed references to Day 3 to note that Day 3 assessments were completed for cohorts 1, 2, and 3 only.	The protocol was revised to remove Day 3 for SAD to consolidate visits and procedures for the subjects. The revision to add a + 1 day visit window to Day 2 is made so that assessments (including the pharmacokinetic [PK] sample) can take place on Day 1 or Day 3 depending on the site or subject's schedule.
Table 1	Added line Observed response for complete closure of TMP as assessed by site investigator and Imputed Response for complete closure of TMP as assessed by site investigator	The tables for complete TMP closure and imputation of TMP closure were changed to include both the site investigator assessment and central reader assessment.
6.5.1	Added TEAEs causing treatment discontinuation (only for MAD and MDE)	These TEAEs are collected for MAD and MDE.

7.2 List of Changes in SAP Version 2.0 from Version 1.0

The changes from the approved SAP Version 1.0 (Dated 23-Mar-2020) to Version 2.0 (Dated 22-Nov-2020) that impact analyses are listed with the rationale in the table below.

SAP Sections	Description	Rationale
6.4, 6.4.3	For the regression analysis of change from baseline in TMP size and mean air conduction hearing at Week 12 treatment group as a classification variable is removed. Also predictor variable is updated as change from baseline in ratio of TMP size per total area of tympanic membrane and response is updated as change from baseline in mean A-B gap.	An improvement in TMP size should improve the air conduction hearing hence the response and predictor variables are reversed. The analysis is to understand the relationship between the response variable and predictor hence the classification variable is removed. Change from baseline in ratio of TMP size per total area of tympanic membrane is used because it is normalized per the total area of tympanic membrane. Change from baseline in mean A-B gap is used because air conduction and bone conduction tests analyzed together determines any hearing loss.
6.5.4	For Modified Brighton Grading Scheme, time intervals Days 2 to 11 is updated as Days 2 to 18, Day 19 to 39 is updated as \geq Days 19. \geq Days 40 time interval is removed.	Provides comparisons across SAD, MAD, single dose expansion and multiple dose expansion in a consistent manner.
6.9.1.1	Details to address duplicate values on the same day for Microscopic ear examination is added.	Missing hence added.
9.1, 9.2, 9.3	For the categorical variable coming from imaging data, updated about addressing duplicates values on the same day as the continuous variables.	For consistency across variables coming from imaging data.
6.9.1.2, 6.9.2.2	Visit Window for Week 2 single dose expansion is updated.	Due to Protocol Version 2.0 (Week 1 is removed).
	Adverse Events of Interest list is revised using MedDRA version 23.0.	Due to MedDRA version update which is updated to capture COVID-19 related terms. The terms in Sections 9.2 and 9.3 remained the same compared to MedDRA version 22.0.

9 APPENDICES

9.1 Appendix 1: Pre-Specified Criteria for Adverse Events of Interest: Cholesteatoma or Neoplasm

All selected terms are based on MedDRA Version 23.0

Neoplasm

1. Aural neoplasms benign (PTs)

Preferred Term Code	Preferred Term
10052241	Aural cystadenoma
10003794	Aural polyp
10069051	Benign ear neoplasm
10004292	Benign middle ear neoplasm
10008649	Cholesterin granuloma of middle ear
10008660	Cholesterol granuloma
10061332	Paraganglion neoplasm

2. Aural neoplasms malignant (PTs)

Preferred Term Code	Preferred Term
10055016	Ear neoplasm
10055017	Ear neoplasm malignant
10082277	External ear neoplasm malignant
10061267	Malignant middle ear neoplasm

Cholesteatoma (PTs)

Preferred Term Code	Preferred Term
10008642	Cholesteatoma

9.2 Appendix 2: Pre-Specified Criteria for Adverse Events of Interest: Ototoxic symptoms (Tinnitus, Sensorineural hearing loss, Dizziness)

All selected terms are based on MedDRA Version 23.0

Ototoxicity symptoms (PTs)

Preferred Term Code	Preferred Term
10043882	Tinnitus
10047340	Vertigo
10013573	Dizziness
10011878	Deafness
10061373	Sudden hearing loss

Ototoxicity (PTs)

Preferred Term Code	Preferred Term
10033109	Ototoxicity

9.3 Appendix 3: Pre-Specified Criteria for Adverse Events of Interest: Otitis media or Otitis externa

All selected terms are based on MedDRA Version 23.0

Middle ear infections (PTs)

Preferred Term Code	Preferred Term
10061557	Allergic otitis media
10078160	Bezold abscess
10081430	Eosinophilic otitis media
10063095	Gradenigo's syndrome
10065838	Middle ear inflammation
10061302	Myringitis
10078830	Noninfective myringitis
10033078	Otitis media
10033079	Otitis media acute
10065176	Otitis media bacterial
10033081	Otitis media chronic
10065175	Otitis media fungal
10067322	Otitis media haemophilus
10033083	Otitis media moraxella
10080507	Otitis media pneumococcal
10033085	Otitis media post measles
10080508	Otitis media staphylococcal
10065177	Otitis media viral
10033102	Otosalpingitis
10034762	Petrositis

External ear infections (PTs)

Preferred Term Code	Preferred Term
10000295	Abscess of external auditory meatus
10075072	Allergic otitis externa
10014014	Ear lobe infection
10015729	External ear cellulitis
10065837	External ear inflammation
10019959	Herpes simplex otitis externa
10063491	Herpes zoster oticus
10033072	Otitis externa
10065179	Otitis externa bacterial
10033076	Otitis externa candida
10052557	Otitis externa fungal
10065178	Otitis externa viral
10062067	Perichondritis

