7.3.6 Adverse Events of Special Interest

Incidence of adverse events of special interest as defined below:

1. Cholesteatoma or ear neoplasm
2. Ototoxic symptoms (tinnitus, sensorineural hearing loss, dizziness)
3. Otitis media or otitis externa

Additional data may be collected for AEs of special interest (i.e., unscheduled microscopic pictures, histopathology, surgical procedures, or other treatments).

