8 DISCONTINUATION

8.1 Discontinuation of Individual Subject(s) From Study Treatment

SAD and single dose expansion

Not applicable because there is a single treatment of ASP0598 Otic Solution or placebo.

MAD and multiple dose expansion

Treatment Discontinuation

During the course of IP administration, if the subject experiences a drug-related adverse event (AE) the IP administration may be discontinued at the investigator's discretion.

In addition, study drug administration will be discontinued if any of the following occur:

- Subject develops cholesteatoma or suspicion of neoplasm in the treated ear as determined by investigator.
- Subjects develops suspected ototoxicity symptoms (e.g., sudden hearing loss at high frequencies (1, 2, 4 kHz), new high frequency tinnitus or new balance disorder) which are considered by the investigator to be related to the study drug.

- Subjects with persistent otitis media or otitis externa unresponsive to oral and topical antibiotics (as described in other area of synopsis)

A discontinuation from treatment is defined as a subject who enrolled in the study and for whom study treatment is permanently discontinued for any reason.

The subject is free to withdraw from the study treatment and/or study for any reason and at any time without giving reason for doing so and without penalty or prejudice. The investigator is also free to discontinue the subject from study treatment or to terminate a subject's involvement in the study at any time if the subject's clinical condition warrants it.

The reason for discontinuation from study treatment must be documented in the subject's medical records.

A subject must discontinue study treatment for any of the following reasons:

- Subject requests to stop treatment.
- Any clinical AE, laboratory abnormality or intercurrent illness, in the opinion of the investigator, indicates continued treatment is not in the best interest of the subject.

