9.5 Analysis of Safety

Safety analysis will be conducted using the SAF, unless otherwise specified.

The primary endpoints to evaluate the safety and tolerability of ASP0598 Otic Solution are shown below:

- TEAEs
- Incidence of AEs of special interest:
 1. Cholesteatoma or ear neoplasm
 2. Ototoxic symptoms (tinnitus, sensorineural hearing loss, dizziness)
 3. Otitis media or otitis externa
- Change from baseline in bone conduction hearing at 1, 2, 4 kHz by PTA
- Change from baseline in TVAS

No statistical hypothesis testing will be performed.

Continuous data will be summarized using descriptive statistics and categorical data will be summarized using number and percentage of subjects.

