9.5.1 Adverse Events

AEs will be coded using MedDRA.

A TEAE is defined as an AE observed after starting administration of the study drug through EOS visit. A drug-related TEAE is defined as any TEAE with a causal relationship assessed as “yes” by the investigator.

An overview of TEAEs and Death by treatment group will be presented. In addition, the following summaries will be presented by SOC and PT:

- TEAEs by treatment group
- Drug-related TEAEs by treatment group
- Serious TEAEs by treatment group
- Drug-related serious TEAEs by treatment group

An overview of TEAEs of special interest by treatment group will be presented. The following summaries will be presented by SOC and PT:

- TEAEs of special interest by treatment group
- Serious TEAEs of special interest by treatment group

Details about selection of AEs of special interest will be provided in the SAP.

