5 EFFICACY AND SAFETY ENDPOINTS

5.1 Primary Safety Endpoint(s)

- Treatment-emergent adverse events (TEAEs)
 - **TEAE:** an AE observed after starting administration of the study drug through end of study visit. If an AE occurs on Day 1 and the onset check box is marked “Onset after the dose of study drug” or the onset check box is left blank, then the AE will be considered TEAE. Refer to Section [6.9.1](#) for end day of end of study visit definition.
 - **Drug-related TEAE:** any TEAE with a causal relationship assessed as “yes” by the investigator. If the relationship is missing then it is considered as drug-related.

Imputed date for AE onset date may be used to determine TEAE (Section [6.9.3.1](#)).

The investigator will use the following definitions to rate the severity of each AE:

- Mild
- Moderate
- Severe

- Incidence of AEs of special interest will be defined as shown below.
 1. Cholesteatoma or neoplasm
 2. Ototoxic symptoms (tinnitus, sensorineural hearing loss, dizziness)
 3. Otitis media or otitis externa

AEs of special interest will be identified using custom MedDRA queries (CMQs). Detailed information about AEs of special interest is provided in Appendices 1, 2 and 3.

- Change from baseline in bone conduction hearing at 1, 2, 4 kHz by Pure Tone Audiometry (PTA)

A lower value indicates better level of hearing.

For the change from baseline, a negative value (decrease from baseline) indicates improvement (i.e., better level of hearing).

Mean bone conduction hearing (dB):

Arithmetic mean of the values at 1, 2 and 4 kHz. If the value is missing for any of the 3 frequencies, then the mean value will be set to missing.

- Change from baseline in Tinnitus Visual Analog Scale (TVAS)

The TVAS is a numeric scale and ranges from 0 (not at all strong or loud) to 10 (extremely strong or loud). A lower value indicates less level of discomfort.

For the change from baseline, a negative value (decrease from baseline) indicates improvement (i.e., less level of discomfort).

TVAS may be reported for one of the following areas: ear (left, right or bilateral) or other.

At a time point, if a subject did not experience tinnitus, TVAS will be reported as 0. In this case, the TVAS will be considered as 0 for all two areas.

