Using the non-missing size of TMP per pars tensa surface area, an observed response is

Yes: if the post baseline size of the TMP per pars tensa surface area $\leq 1\%$ and the size of the TMP per pars tensa surface area is smaller than baseline,

No: if the above condition is false.

Ratio of TMP size per total area of tympanic membrane will be used in the above calculation as an approximation for TMP per pars tensa surface area.

- Change from baseline in Air bone (A-B) gap by PTA

For the change from baseline in A-B gap, a negative value (decrease from baseline) indicates an improvement.

PTA is a behavioral test and generally the 1st quantitative hearing test done to assess the nature and degree of hearing loss in adults and in children.

PTA air conduction and bone conduction tests analyzed together determines any hearing loss: type and magnitude of hearing loss; frequencies that are affected; and whether hearing loss is unilateral or bilateral. For both air and bone conduction, a lower value indicates better hearing threshold.

Type of hearing loss can be as follows:

- Conductive hearing loss: when air conduction thresholds are elevated relative to bone conduction thresholds, an “A-B gap” exists, indicates a conductive hearing loss.
- Sensorineural hearing loss: when air conduction and bone conduction thresholds showing the same amount of hearing loss, indicates sensorineural hearing loss.
- Mixed hearing loss: when both air and bone conduction thresholds are elevated, but air conduction thresholds are more elevated than bone conduction thresholds, indicates mixed hearing loss.

Definitions for mean bone conduction hearing, mean air conduction hearing, mean A-B gap and A-B gap (dB) for each frequency are provided below:

Mean bone conduction hearing (dB):

Arithmetic mean of the bone conduction hearing values at 500 Hz, 1, 2 and 4 kHz. If the value is missing for any of the 4 frequencies, then the mean value will be set to missing.

Mean air conduction hearing (dB):

Arithmetic mean of the air conduction hearing values at 500 Hz, 1, 2 and 4 kHz. If the value is missing for any of the 4 frequencies, then the mean value will be set to missing.

Mean A-B gap (dB):

Mean air conduction hearing - mean bone conduction hearing. If either one is missing or both are missing then the mean A-B gap is set to missing.

A-B gap (dB) for each frequency:

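### The term list for the ototoxicity AESI, part of a primary safety endpoint, has no Preferred Term naming sensorineural hearing loss, one of its three stated components

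*SAP*

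**What the plan says.** Protocol 9.5 introduces its list with "The primary endpoints to evaluate the safety and tolerability of ASP0598 Otic Solution are shown below", and AESI incidence is on that list. Protocol 7.3.6 defines the second AESI group as "Ototoxic symptoms (tinnitus, sensorineural hearing loss, dizziness"; Protocol 3.1 and SAP 5.1 define it the same way.

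The protocol does not list terms. Section 9.5.1 says "Details about selection of AEs of special interest will be provided in the SAP". SAP 5.1 then states "AEs of special interest will be identified using custom MedDRA queries (CMQs" and points to Appendices 1 to 3.

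Appendix 2, headed "Ototoxic symptoms (Tinnitus, Sensorineural hearing loss, Dizziness", gives five terms under ototoxicity symptoms (Tinnitus, Vertigo, Dizziness, Deafness, Sudden hearing loss) and one under ototoxicity (Ototoxicity).

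SAP 6.5.1 builds the AESI overview, and the AESI tables by system organ class and Preferred Term, from these groups.

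**The concern.** The Preferred Term list decides what is counted. The plan names no medical review, investigator flag or audiometric rule that could bring in an event the query misses. Tinnitus and dizziness each have a term of their own name, but sensorineural hearing loss does not. If the coding dictionary has a separate Preferred Term for it, or for hearing loss that is not sudden, an event coded there satisfies the written AESI definition and is still left out of the AESI tables.

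This is a first-in-human study of a drug applied to the eardrum, and the groups are small. The ototoxicity AESI line is where a reader will look first for hearing harm. An undercount there would make the primary safety table disagree with its own definition.

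**Working it through.** The plan gives no figure to reproduce. The check sets the definition against the list and then sizes one missed subject.

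**Components against terms (SAP 5.1 and Appendix 2)**

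| Component | Preferred Terms that address it | Count |
|---|---|---|
| Tinnitus | Tinnitus | 1 |
| Dizziness | Dizziness, Vertigo | 2 |
| Hearing loss, type not stated | Deafness, Sudden hearing loss | 2 |
| General | Ototoxicity | 1 |
| Named as sensorineural hearing loss | none | 0 |

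The total is 1 + 2 + 2 + 1 + 0 = 6 terms.

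**Can the generic term be presumed to cover the specific one?** The SAP's own list-building suggests not. Appendix 3 has 20 middle-ear and 13 external-ear terms, 33 in all. It lists Otitis media and then, separately, its acute, bacterial, chronic, fungal and viral forms, among others. It does the same for Otitis externa. Those entries would be redundant if a generic Preferred Term took in its specific forms. SAP 5.4 also treats the sensorineural type as distinct from conductive and mixed loss: "Sensorineural hearing loss: when air conduction and bone conduction thresholds showing the same amount of hearing loss, indicates sensorineural hearing loss". Nowhere does the SAP say that Deafness and Sudden hearing loss are meant as proxies.

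**Where a missed event would still show**
- SAP 6.5.1 tabulates all TEAEs by system organ class and Preferred Term, so the event appears there.
- SAP 6.5.2 counts subjects with a bone-conduction increase of at least 20 dB, or at least 10 dB at two consecutive frequencies, at each visit and at maximum. A shift of that size appears there.
- No rule carries either result into the AESI tables.

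**Size of one missed subject**

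Active-arm sizes are 4 per SAD cohort, 6 per MAD cohort and 13 per expansion arm (Protocol 4.1 and 6.3.6). SAP 6.5 also presents an ASP0598 total.

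- Single active arm: 1/4 = 25.0%; 1/6 = 16.7%; 1/13 = 7.7%.
- Pooled ASP0598, all arms filled: SAD 4 × 4 = 16, so 1/16 = 6.3%; MAD 2 × 6 = 12, so 1/12 = 8.3%; expansion with two active arms 2 × 13 = 26, so 1/26 = 3.8%.

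These are the weight of one subject. They do not predict how many will be missed.

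**The case against.** The list has support in the protocol. Section 8.1 describes suspected ototoxicity partly as sudden loss at high frequencies, and the stopping rules in 4.1.1.3 speak of acute loss. The term "Sudden hearing loss" fits both; Deafness and Ototoxicity widen the net. A subject who also reports tinnitus, dizziness or vertigo is already counted. Bone conduction at 1, 2 and 4 kHz is itself a primary endpoint and does not depend on coding. Safety carries no hypothesis test, and nothing ties escalation or stopping decisions to the Appendix 2 query.

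All of that stands, and it limits the harm. It does not make the AESI tables match their definition, which says sensorineural hearing loss and does not restrict it to sudden loss.

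A reader might infer three stronger things that the documents do not support:

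- *That only total or abrupt hearing loss is covered.* Appendix 2 gives codes and names only. It does not say that Deafness is limited to total loss, or which reported terms are coded to it. Some sensorineural cases may well land there.
- *That such losses would vanish from the report.* The overall TEAE tables and the bone-conduction summaries would still show them.
- *That leaving out balance disorder is the same error.* Protocol 8.1 does mention "new high frequency tinnitus or new balance disorder", but as an example in a treatment-discontinuation criterion. Balance is not in the three-part AESI definition, so adding balance or vestibular terms is optional.

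**Conclusion.** The point holds in a limited form. A named component of a primary safety endpoint has no Preferred Term of its own in the query that defines the count. The plan neither adds one nor states which listed terms stand in for it. As written, the ototoxicity AESI incidence can be too low.

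One missed subject moves the incidence by about 8 to 25 percentage points in a single active arm and by about 4 to 8 points in the pooled ASP0598 column. The pooled range assumes that all arms fill and that the expansion has two active arms.

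The conclusion rests on two assumptions: that the custom queries are the only selection route, since no other is described, and that the coding dictionary has at least one relevant hearing-loss Preferred Term outside the six. The second cannot be confirmed from the documents, so the number of events at risk is unknown and may be zero.

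**What to change.** Before database lock, search the MedDRA version used for coding. Add to Appendix 2 the Preferred Term or terms to which sensorineural hearing loss, and hearing loss not described as sudden, are coded. If the search shows that these are already coded to a listed term, record that in the appendix so that the coverage is explicit. SAP Section 1 requires changes affecting dose escalation to be approved before that phase is unblinded for its interim analysis, so note in the revision history which phases the updated list applies to.

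There is no need to repeat the SAP 6.5.2 shift results in the AESI table.

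The cost is a dictionary search and an appendix edit. The counted ototoxicity incidence may rise slightly.
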